5.3. Exclusion criteria

History of head trauma

Substance misuse other than nicotine.

Pregnancy. Female patients will take a urine pregnancy test before the beginning of the TMS sessions and they will be required to use contraceptive methods during the **study** in order to enroll in the study. In case of a suspicion of a pregnancy during the **study** despite the use of contraceptives a urine test will be taken.

TMS specific criteria (exclusion criteria)

Past history of epilepsy

Other increased neuronal activity in Electroencephalography (EEG). EEGs of all patients will be recorded before the beginning of TMS. Patients displaying abnormal EEG findings will be excluded.

MRI contraindications, since such an examination maybe necessary in case of adverse reactions.

6. Assessment of effectiveness

6.1. Effectiveness parameters: measuring methods and reference dates

The efficacy of TMS sessions will be evaluated primarily as improvement in SRRS baseline score after treatment. Furthermore, we investigate the effect of TMS on gross motor behavior (SRRS, actigraphy), fine motor function (finger tapping test), and hand gesture performance (TULIA). To this purpose, clinical ratings will be assessed twice, at baseline and after the last TMS **session**. Furthermore, changes may be demonstrated by the scales assessing the disorder specific symptoms; in patients with major depressive disorder, HAMD, MADRS and BDI, in patients with schizophrenia PANSS, SANS, CAINS and the Bush Francis Catatonia Rating Scales. Statistical analysis will comprise repeated measures ANOVAs of motor variables and stimulation mode as between subject variable. Clinical response will be defined as a 30% reduction of the SRRS scores.

7. Assessment of safety

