4.1. Targeted primary end point and secondary end points (effectiveness and safety parameters)

Main objective is the effect of TMS on psychomotor retardation (PR) in patients with major depressive disorder or schizophrenia. Primary outcome marker will be the change in psychomotor performance as assessed by Salpêtrière Retardation Rating Scales (SRRS). Clinical response will be defined as a 30% reduction of the SRRS baseline scores.

Secondary targets will be the effect of TMS on other motor parameters and on specific symptoms e.g. depressive or negative symptoms.

Efficacy parameters: TMS parameters may be of critical role determining the effect of the applied TMS on motor symptoms.

Safety parameters: As specific safety factors in relation to TMS, patients with 1. past history of epilepsy, or 2. other increased neuronal activity in Electroencephalography (EEG), 3. MRI contraindications and 4. substance misuse will be excluded. EEG recordings will be held for all patients before the beginning of TMS. Patients will be screened every 5 sessions with SRRS and actigraphy. In case of moderate deterioration of motor performance (30% change of initial ratings of SRRS or/and actigraphy) or adverse reactions during the TMS protocol, patients will be excluded from further participation in the study. .

4.2. Specification of the parameter that is of primary interest and other parameters that will be assessed as additional, secondary end points.

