The complete stimulation details are given in section TMS Protocol. Regardless of the type and the frequency of TMS, the **stimulation** protocol will consist of 15 daily sessions during a 3 week period. The ratings mentioned above will be repeated after the end of the TMS.

Tabular overview

Selection of participants	Information about the procedure and the goals of the study
	Written informed consent is obtained
	Specific safety parameters for TMS sessions will be assessed
	EEG Recordings
	Bern Psychopathology Scales (BPS) for the assessment of motor activity levels
	Mini-International Neuropsychiatric Interview (MINI)
Assessment before TMS	Actigraphy
	Salpêtrière Retardation Rating Scales (SRRS)
	Finger tapping test
	Test of Upper Limb Apraxia (TULIA)
Specific assessment: patients with Major Depressive Disorder	Hamilton Rating Scale for Depression (HAMD)

	Montgomery Åsberg Depression Rating Scale (MADRS)
	Beck Depression Inventory (BDI)
Specific assessment: patients with schizophrenia	Positive and Negative Syndrome Scales (PANSS)
	Scales for the Assessment of Negative Symptoms (SANS)
	Clinical Assessment Interview for Negative Symptoms (CAINS)
	Bush Francis Catatonia Rating Scales (BFCRS)
Transcranial magnetic stimulation	Randomized allocation to four equal groups
	15 daily sessions (3 week period)
Assessment after TMS	Repetition of the assessments taken place before TMS

Course of the study

The study will be started immediately after ethical approval. Subject recruitment, testing and data analysis will last approximately 36 months.

The study will encompass the following periods:

Preparation (2 months)

At this period, the rater will be trained using the rating scales and the assessment methods. Additionally, the various departments of the clinic will receive detailed information on the study, while the function of all technical equipment and its' response to the design of the study will be tested. Modifications, if necessary, will be made.

Subject recruitment, ratings, TMS sessions and repetition of ratings (24 months)

During this phase, patients will be motivated to participate in the study. As the recruitment and screening of individuals will be taking place, TMS will be performed continuously during this period. Patients will be reassessed after every 5 sessions and in the end of the TMS. Contemporaneously, the data of the rating scales and methods will be digitalised and prepared for statistical analyses.

Analyses and publication (10 months)

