7.1. Safety parameters: measuring methods and times

Specific safety parameters for TMS include: past history of epilepsy, pregnancy, other increased neuronal activity in Electroencephalography (EEG), MRI contraindications and substance misuse other than nicotine. Female patients will take a urine pregnancy test before the beginning of the TMS sessions and they will be required to use contraceptive methods during the **study** in order to enroll in the study. In case of a suspicion of a pregnancy during the **study** despite the use of contraceptives a urine test will be taken. These parameters will be observed and are explicit exclusion criteria. EEGs of all patients will be recorded before the beginning of TMS. Patients displaying abnormal EEG findings will be excluded. The rest of above mentioned parameters will be as well observed and are explicit exclusion criteria. After every 5 sessions, assessments of gross motor behaviour (SRRS,

actigraphy) will be repeated. In case of moderate deterioration of motor performance (30% change of initial ratings) patients will be excluded from the **study**.

7.2. Guarantee of follow-up examination of patients in case of adverse reactions.

The study will be carried out according to the protocol. In case of serious adverse events, which may be connected to the TMS **stimulation** or any relevant assessments (Art.42, KlinV), the Ethics Committee will be as soon as possible informed by the sponsor. Serious adverse events may include seizures or exacerbation of psychiatric symptoms. In such cases the TMS sessions will be immediately stopped and the patient will be excluded from the study. A MRI examination will be held and any necessary additional medical consultations will be arranged.

8. Statistics

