8.5. Handling of missing data, dropout cases

Only complete data records with assessments at two time points will be entered in the analyses. In case of dropout we will perform an intention-to treat (ITT) analysis applying the last-observation-carried-forward method (LOCF). In case of revocation of patients (KlinV, Art.9), data will be anonymized.

9. Study-specific safety precautions and responsibilities

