9.1. Safety precautions

The specific risks for TMS include past history of epilepsy, pregnancy, other increased neuronal activity in Electroencephalography (EEG), MRI contraindications and substance misuse other than nicotine. EEGs of all patients will be recorded before the beginning of TMS. Patients displaying abnormal EEG findings will be excluded. Female patients will take a urine pregnancy test before the beginning of the TMS sessions and they will be required to use contraceptive methods during the **study** in order to enroll in the study. In case of a suspicion of a pregnancy during the **study** despite the use of contraceptives a urine test will be taken. The rest of above mentioned parameters will be as well observed and are explicit exclusion criteria.

After every 5 sessions, assessments of gross motor behaviour (SRRS, actigraphy) will be repeated. In case of moderate deterioration of motor performance (30% change of initial ratings) during the **study**, patients will be excluded from the TMS. The investigators are responsible for the observation of the above mentioned criteria and the screening of patients. Patients will have to provide written informed consent, which will include explicit questions referring to the exclusion criteria. The safety criteria will be asked again before the beginning of TMS **sessions** and participants will have to warrant that none of the exclusion criteria is fulfilled.

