9.2. If appropriate: exit examination in case of dropout

At the end of every week of the **TMS stimulation**, assessments of gross motor behaviour (SRRS, actigraphy) will be repeated. In case of moderate deterioration of motor performance (30% change of initial ratings), patients will be excluded from the **study**. In case of seizures or persisting headaches a Magnetic Resonance Imaging Examination will be held for diagnostic purposes.

10. Duties of the investigator

10.1. Confirmation that the conduct of the study will be in accordance with the GCP protocol, the current legal regulations and rights.

Hereby investigators confirm that they have knowledge of the GCP protocol, according to which the study will be carried out. All current legal regulations and rights will be additionally taken into account.

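### The timing of SRRS and actigraphy is stated inconsistently, and the efficacy plan does not say how in-treatment ratings count for patients who leave early

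*Combined protocol and SAP*

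**What the plan says.** **Two ratings.** Section 6.1, on effectiveness, names SRRS and actigraphy and then states that "clinical ratings will be assessed twice, at baseline and after the last TMS" session. The project summary in section 3, and sections 3.2 and 4.2, give the same two times for clinical ratings. Section 8.1 gives them for actigraphy. The tabular overview in 4.3 has one post-baseline row, "Repetition of the assessments taken place before TMS". The time budget in 4.3 lists 210 minutes before TMS, 450 minutes of sessions and 210 minutes after.

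**Repeated ratings.** Section 4.1, under safety parameters: "Patients will be screened every 5 sessions with SRRS and actigraphy". Section 4.3, course of the study: "Patients will be reassessed after every 5 sessions and in the end of the TMS". Section 9.1: "After every 5 sessions, assessments of gross motor behaviour (SRRS, actigraphy) will be repeated"; 7.1 says the same. Section 9.2 sets the same assessments "At the end of every week of the" stimulation.

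**Use of the ratings.** In 4.1, 7.1, 9.1 and 9.2 a 30% deterioration leads to exclusion. For efficacy, 8.3 compares response (more than 30% SRRS improvement) by Chi² tests. It analyses motor variables by repeated-measures ANOVA without naming the time points, and adds an ANCOVA on ratings before and after TMS. Section 8.5 begins "Only complete data records with assessments at two time points will be entered in the analyses" and then prescribes an intention-to-treat analysis with LOCF for dropouts.

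**The concern.** SRRS is both the primary measure and the trigger for withdrawal, so the in-treatment ratings explain why some patients have no end-of-treatment value. The plan requires these ratings in several places, leaves them out of the overview table and time budget, and gives them no stated role in any efficacy analysis.

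What is at stake is the outcome assigned to patients who leave early. The two sentences of 8.5 point in different directions: one removes such patients and the other keeps them with a carried value. Nothing says whether that value is the last in-treatment rating or baseline. The choice can remove or conceal the deterioration that caused the withdrawal, and it can decide whether a patient who left early counts as a responder.

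**Working it through.** **1. The plan's own figures.** Time budget: 30 × 15 = 450 minutes, and 210 + 450 + 210 = 870 minutes. This reproduces, and it contains no line for in-treatment ratings. Sample size (8.2): w = √[((0.40 − 0.25)² + (0.10 − 0.25)²)/0.25] = √0.18 = 0.424. With N = 79, λ = 79 × 0.18 = 14.22; against the critical value 7.815 on 3 df, power is 0.901. This also reproduces, and nothing below depends on it.

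**2. How many schedules there are.** 15 sessions / 3 weeks = 5 sessions a week.

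| Wording | Post-baseline ratings fall after session |
|---|---|
| Before and after TMS (6.1, table, time budget) | 15 |
| Every five sessions (4.1, 4.3, 7.1, 9.1) | 5, 10, 15 |
| Weekly (9.2), sessions as planned | 5, 10, 15 |
| Weekly (9.2), if only 4 sessions a week are held | 4, 8, 12, … |

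As planned there are two schedules: two SRRS ratings, or four including baseline. They differ by the ratings after sessions 5 and 10. The weekly wording separates from the five-session wording only when sessions are missed or shifted.

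**3. Ratings with no named efficacy role.** 80 patients × 2 = at most 160 SRRS ratings and 160 actigraphy readings. This is a ceiling that assumes nobody leaves early.

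**4. What each rule does to a patient who leaves.** Assume no rating is made after withdrawal. Patient A is withdrawn after session 10 with SRRS 30% worse. Patient B leaves after session 10 because of an adverse reaction, with SRRS 35% better. Both are illustrations.

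| Rule | A: SRRS change | A: response | B: SRRS change | B: response |
|---|---|---|---|---|
| Complete records (baseline and end of TMS) | dropped | dropped | dropped | dropped |
| LOCF, in-treatment value | +30% | no | −35% | yes |
| LOCF, baseline value | 0% | no | 0% | no |

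**5. Size in an arm of 20.**
- Patient A, in-treatment against baseline carried: 30/20 = 1.5 percentage points in the arm's mean SRRS change. The documents give no expected number of withdrawals. For one to four such patients the difference is 1.5, 3.0, 4.5 or 6.0 points.
- Patient A dropped against in-treatment value carried: if the other 19 patients average a change of m%, the difference is m − (19m + 30)/20 = (m − 30)/20. That is −1.5 points at m = 0 and −3.0 points at m = −30, so dropping the patient makes the arm look better.
- Patient B: 1/20 = 5 points in the response rate at the end of the trial. At the first interim look, 25% of 80 = 20 patients, or about 5 per arm, so 1/5 = 20 points. Section 8.3 allows an arm to be stopped at that look.

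**The case against.** The strongest reply is that 6.1 deals with effectiveness, so two ratings there can mean the efficacy ratings only, while the repeats sit mainly under safety. Every passage agrees on a baseline rating and one after the last session, so the endpoint visit is not in dispute. LOCF would naturally carry the last in-treatment SRRS, and the repeated-measures ANOVA in 8.3 is not expressly limited to two times.

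Much of this stands, and it limits the point:
- A reader might infer three competing schedules. At five sessions a week there are two.
- A reader might infer that the in-treatment ratings are unused. They drive the deterioration rule and may feed LOCF; what is missing is any stated efficacy use.
- A reader might infer that the safety check will be missed because the table omits it. This is a single-site trial, five sections require the repeats, and the course-of-study text follows the table. The documents do not support that prediction.
- A reader might infer that the primary measure is collected at different times in different patients. For baseline and end of treatment, the documents do not say that.

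What the reply does not settle is 8.5. No passage calls the in-treatment ratings safety-only, and 4.3 states them as part of the general course of the study. The value that LOCF carries remains undefined beside a sentence that admits two time points only.

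**Conclusion.** The point holds as an inconsistency in timing plus a gap in the analysis plan. The size depends on how many patients leave early, which the documents do not state. Per patient in an arm of 20 it is 1.5 points of mean SRRS change between the two LOCF readings for a 30% deterioration. For someone who leaves after responding it is 5 points of response rate. These figures assume no rating after withdrawal and, for the first, that SRRS itself worsened by 30%; section 4.1 also lets actigraphy trigger withdrawal.

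For a deteriorated patient, the choice between the two carried values does not change responder status; it matters for the continuous analysis. The responder definition, the sample size of 79 and the stated power are unaffected. With complete data, using the extra visits would gain little; the benefit lies in patients who leave early.

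**What to change.** 1. Reconcile 6.1, the tabular overview, the time budget, 7.1, 9.1 and 9.2 on when SRRS and actigraphy are rated. The schedule of the deterioration check is for the investigators to settle; this review does not choose it.
2. In 8.3 and 8.5, replace the two-time-point/LOCF repeated-measures ANOVA of SRRS and actigraphy with a mixed model that uses every collected visit. Make the between-arm contrast at the end of treatment the effect of interest. The model then includes the ratings that triggered withdrawal.
3. In 8.5, state which SRRS value LOCF carries for the responder endpoint, and how that rule fits with the sentence on two time points. The mixed model does not answer this, because it applies only to the continuous measures.

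The cost is protocol wording and one extra model specification; 4.1, 7.1 and 9.1 already require the data. The model also brings a missing-at-random assumption. That is plausible when a recorded rating triggers withdrawal, and less secure when a patient leaves for an adverse reaction that the ratings do not reflect.

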8.1. Definition of the primary end point and secondary end points

Primary outcome of the study will be clinical response as defined by >30% improvement from the baseline score of the Salpêtrière Retardation Rating Scales (SRRS). Moreover, gross motor behavior (actigraphy), fine motor function (finger tapping test), and hand gesture performance (TULIA) will be assessed at baseline and after the last TMS. Furthermore, we will investigate the efficacy of TMS on disorder specific symptoms; in patients with major depressive disorder, HAMD, MADRS and BDI, in patients with schizophrenia PANSS, SANS, CAINS and the Bush Francis Catatonia Rating Scales will be carried out before and after TMS. Statistical analysis will comprise ANOVAs of motor variables and stimulation mode as between subject variable. Clinical response will be defined as a 30% reduction of the SRRS scores. Frequency of response will be compared between groups using Chi²-Tests.

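### Patients who stop TMS early have no scheduled assessment on nine secondary outcomes, and section 8.5 gives two conflicting rules for them, each of which loses any worsening

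*Combined protocol and SAP*

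**What the plan says.** Section 6.1 states that "clinical ratings will be assessed twice, at baseline and after the last TMS" session. Section 8.1 gives the same timing for the fine-motor and gesture tests ("fine motor function (finger tapping test), and hand gesture performance (TULIA) will be assessed at baseline and after the last TMS") and for the disorder-specific scales ("PANSS, SANS, CAINS and the Bush Francis Catatonia Rating Scales will be carried out before and after TMS"); the latter sentence also covers HAMD, MADRS and BDI. The tabular overview in 4.3 agrees: the baseline set is repeated once, after TMS.

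Between those points, sections 4.1, 7.1 and 9.1 (every 5 sessions) and 9.2 (weekly) provide a check in which "assessments of gross motor behaviour (SRRS, actigraphy) will be repeated". The course-of-study text in 4.3 also mentions reassessment every 5 sessions but names no instrument.

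Section 9.2 carries the heading "If appropriate: exit examination in case of dropout". Its text holds the routine weekly check, the exclusion rule for a 30% deterioration, and one event-triggered examination: "In case of seizures or persisting headaches a Magnetic Resonance Imaging Examination will be held for diagnostic purposes". Section 7.2 adds only an MRI and medical consultations after serious adverse events.

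Patients are removed for motor deterioration or adverse reactions (4.1, 7.1, 9.2) and for serious adverse events, which may include psychiatric exacerbation (7.2, 10.2). Those sections remove them from the study. Section 9.1 removes deteriorating patients from the TMS.

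Section 8.5 first restricts the analyses to records complete at both time points. Its next sentence reads: "In case of dropout we will perform an intention-to treat (ITT) analysis applying the last-observation-carried-forward method (LOCF".

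**The concern.** Removal depends on how the patient is doing, and removal also ends measurement on the scales that would show it. A patient withdrawn for psychiatric exacerbation has a baseline PANSS or HAMD and nothing later. The analysis then either leaves that patient out or enters no change, and neither describes what happened.

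Three parts of the plan depend on these values: aim (c) in 3.1, on depressive and negative symptoms; the fine-motor and gesture parts of aim (a); and the ANCOVA in 8.3, which uses change in symptom ratings as a covariate to separate motor benefit from general clinical response. If stops differ between arms, as they may with three different active protocols and a sham, the arm comparisons can be biased.

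**Working it through.** **The plan's own figure.** The plan states no dropout rate and no figure on this point. Its sample size reproduces: w² = (0.15² + 0.15²)/0.25 = 0.18, λ = 79 × 0.18 = 14.22, power 90.1%. It concerns the response endpoint and does not depend on what follows.

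**Step 1: what has been measured when a patient stops.**

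| Outcome | Before | Interim (every 5 sessions) | After | Value LOCF carries for an early stop |
|---|---|---|---|---|
| SRRS, actigraphy | yes | yes | yes | latest interim value; baseline only if stopped before the first interim rating |
| Finger tapping, TULIA | yes | no | yes | baseline |
| HAMD, MADRS, BDI (MDD) | yes | no | yes | baseline |
| PANSS, SANS, CAINS, Bush-Francis (schizophrenia) | yes | no | yes | baseline |

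For the nine outcomes in the last three rows, the LOCF change is baseline minus baseline, which is 0.

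**Step 2: what each rule in 8.5 does to an arm mean.** Let d be the fraction stopped, μc the mean improvement of completers, and μs the mean improvement that stopped patients would show at the planned date.

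- Mean over all randomised patients: (1−d)μc + dμs
- LOCF: (1−d)μc, so the error is −dμs
- Deletion: μc, so the error is d(μc − μs)

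If stopped patients worsened (μs < 0), both errors are positive and the arm looks better than it was. If they would have improved like the others (μs = μc > 0), deletion is unbiased and LOCF makes the arm look worse.

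**Step 3: illustration with LOCF.** Assume μc = μs = 0.8 SD in both arms.

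- 5% stopped: 0.8 × 0.95 = 0.76
- 20% stopped: 0.8 × 0.80 = 0.64; false difference 0.76 − 0.64 = 0.12 SD
- 30% stopped: 0.8 × 0.70 = 0.56; false difference 0.76 − 0.56 = 0.20 SD

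At 20 per arm these rates are 1, 4 and 6 patients. The standard error of a two-arm difference is √(2/20) = 0.32 SD, so the false differences are about 0.4 and 0.6 of a standard error. That standard error suits finger tapping and TULIA. The disorder-specific scales are given to one diagnosis only, so fewer patients contribute and it is larger.

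**Step 4: simulation under LOCF** (20 per arm, change SD 1, two-sided t-test at 0.05, 40,000 runs; all rates assumed).

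- No true difference, stops of 5% against 25%: a common improvement of 0.5 SD gives a spurious 0.10 SD and type I error of 6.4%; 1 SD gives 0.20 SD and 10.2%; none gives no bias and 5.1%.
- True difference 0.9 SD, equal stops: the difference shrinks to 0.9 × 0.90 = 0.81 SD at 10% and 0.9 × 0.80 = 0.72 SD at 20%. Power falls from 79% to 65–74% and 53–67%, for common improvements from 1 SD down to 0.

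**Step 5: the ANCOVA in 8.3.** For a patient stopped after session 5 or 10, LOCF gives SRRS an interim value while the symptom-change covariate is set to 0. The two no longer refer to the same period. Under deletion the patient leaves this analysis.

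**The case against.** A reader might infer that every stopped patient is analysed as unchanged, that harm is hidden, and that the main result is compromised. The documents do not support this.

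- **Zero change is one of two readings.** The first sentence of 8.5 would delete a baseline-only record. The plan does not say which rule governs.
- **A post-TMS rating is not ruled out.** The phrase in 6.1 could mean the last session received, and 9.1 removes deteriorating patients from the TMS only. But 4.1, 7.1, 7.2, 9.2 and 10.2 remove patients from the study, and no section says the battery is done for them. If it were, ratings after different numbers of sessions would be analysed as one time point.
- **The primary endpoint is largely outside the point.** SRRS is repeated every 5 sessions, and a patient removed for SRRS deterioration has that value on record for LOCF to carry. The exception is a patient who stops before the first interim rating.
- **Safety reporting is not silenced.** Serious adverse events, including psychiatric exacerbation, go to the Ethics Committee (7.2, 10.2). What is lost is their contribution to mean change on secondary scales.
- **The numbers are hypothetical.** The 0.8 SD and the stop rates are all assumed, and the illustration has stopped patients improving like the rest. It therefore does not model erased worsening, which acts in the opposite direction.

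These objections limit the scope and the certainty. They leave standing the missing assessment and the contradiction in 8.5.

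**Conclusion.** The point holds for the nine secondary outcomes measured only before and after the course. The plan schedules no assessment on them for a patient who stops early, and the two rules in 8.5 conflict. Deletion and LOCF both discard any worsening, and LOCF also biases the comparison when stopped patients would have improved.

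Under the assumptions in step 3, the LOCF bias is 0.12 to 0.20 SD, modest against the sampling error at this sample size. The bias from erased worsening cannot be sized from the documents. This should be corrected before data collection, because the missing values cannot be recovered afterwards. It is not a threat to the primary SRRS comparison.

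**What to change.** **Sections 6.1 and 9.2.** For outcome assessment, separate stopping TMS from leaving the study, and reconcile 4.1, 7.1, 7.2, 9.2 and 10.2 with 9.1. This takes no position on when stimulation should stop. Every randomised patient who has not revoked consent completes the post-TMS battery with the blinded rater at the originally planned post-course date, about 3 weeks after session 1. That date becomes the fixed analysis time point. Because 4.3 allows the allocation envelope to be opened after adverse reactions, state that the rater is not told its content.

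**Section 8.5.** Remove the contradiction. Use the observed values in the ITT analysis. Do not apply LOCF to a scale whose only earlier value is baseline. For values still missing, use a likelihood-based model and state its missing-at-random assumption. With only baseline to condition on, such a model cannot recover worsening that caused the stop, so add a sensitivity analysis that lets stopped patients do worse.

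**Cost.** Protocol wording, plus one 210-minute battery for each patient who has stopped. Section 4.3 already budgets this battery for every participant. Some of these patients may be unwell or may decline.
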